- **Study Sites:** We will recruit patients from 3 hospitals: UVM, JHU and UCLA. These sites were selected due to successful prior collaborations, experience in ICU RCT recruitment, similar sedation practice (Prelim Data 6), experience in ICU mobility/actigraphy, and similar “usual care” (Prelim Data 6). A study overview is in Figure 3.

- **Data Coordinating:** Data coordination will occur through integrated efforts between Healthy Design and all 3 study sites, with full support for design, conduct, monitoring, and analysis. An employed data coordinator will create a study database in RedCAP

and will manage data from all 3 enrolling sites. Data coordination, cleaning, and subsequent analyses will be overseen by Drs. [name] (PhD biostatistics faculty/ co-I) with Drs. [name], [name], and [name]. [name] will oversee RCT conduct, including regulatory/ NIH reports. And employed study monitor will conduct site monitoring visits during the RCT.

- **Study Leadership of RCT:** To address leadership and communication issues, an Executive Committee (“EC”: Drs. [name], [name], and [name], along with [name] [Project Manager, UVM]) will meet twice monthly by phone to discuss RCT conduct. For issues that require broader input, the RCT also will have a Steering Committee that includes the EC plus Drs. [name] (UCLA site PI), [name] (Biostatistician), [name] (Nurse co-investigator), [name] (aging/delirium co-investigator) that will meet monthly or as needed. Each site-PI will supervise daily operations, along with site research staff supported by per-patient capitation payments. All investigators will co-author publications, with author order mutually agreed upon in advance.
- **Patients (n=54):** Eligibility criteria are identical to the cohort study in Aim 2 (Table 5).
- **Consent:** As in the study in Aim 2 (STTR Phase I), consent will most often occur via LARs with participant re-consent upon regaining capacity. See below under section on Consent.
- **Randomization:** After consent, patients will be randomized (1:1) to Group A vs B (Fig. 4) via UVM’s web-based system (24 hrs/day), with variable-sized blocks of 2 or 4, stratified by site.

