- **Blinding:** Due to the nature of restraint devices, we cannot blind patients, families, or ICU clinicians. To minimize bias, the primary outcome (actigraphy) will be analyzed by an outcome assessor blinded to patient identity or study group ([name]) and key co-interventions will be standardized with planned analyses to evaluate balance between groups (see Statistical Analysis Plan).
- **Standard ICU co-interventions for all patients:** Important aspects of routine care will be standardized for BOTH study groups based on existing protocols at all sites, including: 1) turning by RN every 2 hr while in bed; 2) sedation/delirium management as per published practice guidelines (see Preliminary Data #6); 3) daily spontaneous breathing trials and ventilator weaning protocols, and 4) nutrition as per registered dietician consultation. These co-interventions are recorded electronically to easily facilitate the study monitoring plan.
- **On-study data collection:** Demographic, laboratory, physiological, and rehabilitation data will be collected (see Tables 5 and 6).

Table 5: Patient Variables -- Collected at Enrollment

Patient Variables – collected at enrollment/baseline	Collection Method	Measurement Scale
Demographic data (e.g. age, sex, race, marital status)	Chart review	Continuous/Binary/Categorical
Height & weight; body mass index	Chart review	Continuous
Comorbidities: Charlson ^a & Functional Indices ^b	Chart review	Ordinal
Baseline function: Katz Activities of Daily Living, ¹¹ and Clinical Frailty Scale ¹²	Proxy interview (see Outcomes below)	Continuous/Ordinal
ICU admission diagnosis (e.g. sepsis, renal failure)	Chart review	Categorical
Severity of illness: APACHE II ^d	Chart review	Continuous
Alzheimer’s disease and related dementia: IQCODE-SF survey ^e ; Delirium Risk Score	Chart review;	Categorical

^aCharlson Index: a score for in-patients derived from 19 comorbidities; an increased score reflecting increased 1-year mortality.¹³

^bFunctional Comorbidity Index: an 18-diagnosis scale for ICU patients predicting 1-year SF-36 physical function.¹

^dAPACHE II: Severity index using age, medical conditions, & acute physiology. Scores reflect increased short-term mortality.¹⁴

^eIQCODE-SF (Short Form of Informant Questionnaire of Cognitive Decline in the Elderly) is a validated proxy-based measure of baseline cognitive impairment commonly used in studies of hospitalized and critically ill patients¹

[figure not shown]

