which time they will be observed by research and nursing personnel, with validated and reliable hourly assessments of sedation/agitation (RASS score). A digital video camera will be set up at the foot of the patient's bed to continuously record his/her movements during the study sessions. Overnight between study Days 1-2 and 2-3, subjects will resume traditional wrist restraints, as per MD order. No sensor or video data will be recorded during overnight periods when study staff are not available. Starting on Day 3 morning, subjects who continue to require restraints (per MD order) will be placed in either traditional or novel restraints device, as per their original randomization (i.e. the device worn for first 4-hr study period on Day 1) for up to 4 more days (i.e. until earliest of restraints no longer needed, death, or ICU discharge). This novel within-patient crossover design allows for increased precision with fewer subjects (see Sample Size) because it controls for confounding effects of patient-specific characteristics via each patient serving as their own control when comparing outcomes (i.e. arm activity) of the novel vs. traditional restraint during Days 1 and 2, along with reduced bias due to randomized allocation of initial study group (novel vs. traditional). Moreover, this design permits more prolonged comparison of novel vs. traditional device (over Days 3 to 6) to measure secondary outcomes (e.g., agitation, delirium, and medication use) that are more accurately evaluated over longer periods of evaluation. The randomization feature of this study design also controls for potential temporal differences in movement (e.g., patient more awake/mobile from 9am-1pm vs. 1pm-5pm). Patient eligibility criteria also help ensure that the study occurs when patients require restraint and are readily assessed for the primary and secondary outcome measures.

- Recurrence of clinical need for restraint and/or ICU readmit:** If a patient ceases to need restraint during the 6-day study period, but then is deemed to need restraint again, the randomly allocated intervention will resume (up to 6-day maximum), with study ending upon ICU discharge (without re-starting if ICU re-admit).

Table 7: Primary & Secondary Outcomes of Efficacy RCT in Aim 3

Outcome		Instrument	Scale	Assessment Timing
Primary Outcome				
1	Upper extremity mobility	Actigraphy (total activity counts per 4 hours)	Continuous	Continuously throughout study
Secondary Outcomes				

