- **Sample size:** Sample size was determined for the primary outcome, arm activity, as assessed by actigraphy over Days 1 and 2 (defined as total activity counts per 4-hour period: 9am-1pm and 1pm-5pm). Although Phase II is 24 months long, there are only 18 months for recruitment, as we need 3 months for startup and 3 months for close out (Table 10). Across the 3 study sites, we expect to recruit 1 patient per site per month during the 18-months, yielding a total N=54. Experience enrolling ICU patients in RCTs at each site.¹ suggests that 1 patient/month/site is feasible and mirrors empirical data, with our analysis of 33,106 patients from 23 RCTs, demonstrating median (IQR) enrollment of 0.90 (0.50–1.79) patients/month per site.²⁰

Assuming N=54, we calculated the treatment effect (i.e. the relative change in the median total activity) that can be detected with 80% power and 5% Type I error rate. We used the following assumptions (these data were informed by our preliminary data with modest adjustments for expected differences for the proposed 3-center study): (1) 9am-1pm median total activity = 3000, (2) 1pm-5pm median total activity = 2700, (3) variance of Log(total activity) set conservatively to 2.5 and 6.0 for 9am-1pm and 1pm-5pm periods, respectively, (4) Log(total activity) has 0.85 correlation within a patient over time, and (5) no cross-over effect of the restraints. Using N=10,000 simulation, the 54-patient sample size can

detect a 56% relative increase in median total activity comparing the novel vs. traditional restraint (median of 3000 vs. 4674).

- **Statistical Analysis Plan**

a) Summary for all Aims: All analyses **will follow the intention-to-treat (ITT) principle**. A 2-tailed p-value <0.05 will be statistically significant. As described in the Study Design (Section 3K), the within-patient crossover design removes patient-specific effects from evaluation of the treatment effect. Potential pitfalls of this design include order effects, carryover effects, and patient dropout. To avoid order effects, we randomize whether patients start the trial with the novel vs. traditional restraint (Figure 4). Carryover effects (i.e. one part of the study affecting subsequent parts) and drop out considerations are discussed further below.

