Subgroup analysis will be performed in eligible patients with baseline history of Alzheimer's disease and related dementia. To evaluate the potential effect of time-varying patient factors (not strictly controlled via a within-patient crossover design – e.g. organ failure status (Table 7)) on the primary results, sensitivity analysis of the above regression results will be conducted by including such variables into regression models. **To evaluate for any sex-specific effect in this study, sex will be included in the regression model as a co-variate and as a statistical interaction term with the main term for treatment (A vs. B) to fully address NIH requirements.**

b) Minimizing missing data: Our primary outcome is assessed during the first 2 study days when missing data are uncommon in our prior studies.¹ Missing data will be minimized through ongoing contact with participants/families and ICU nurses to increase likelihood of obtaining data. Missing data will be described for all variables, and patient characteristics will be compared between those with vs. without missing outcomes.¹ Based on our preliminary data and experience with other studies using similar eligibility criteria, we expect <5-10% missing data due to death or other patient loss, and any missing will not be associated with treatment allocation; thus, no imputation will be performed and we would enroll up to 60 total patients, if needed, to compensate for missing data to obtain the primary outcome on N=54 patients.

c) Data safety monitoring board (DSMB) meetings: The DSMB (see Data Safety document) will meet before the RCT (in STTR Phase II) begins, and after half of the patients have been enrolled into the RCT to review safety and recruitment data only. As this is a small RCT, there will be neither interim analyses to evaluate efficacy nor stopping rules for efficacy or futility.

For research involving survey, questionnaires, etc.: Describe the setting and the mode of administering the instrument and the provisions for maintaining privacy and confidentiality. Include the duration, intervals of administration, and overall length of participation. (describe and attach all instruments)

Not applicable

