All subjects will be informed of the research nature of the activity, including the completion of any measures and questionnaires, the estimated time required to complete the activities, and that participation is voluntary, without any compromise on the current medical care if they decline participation. All study personnel will be trained in the protection of human subjects and HIPAA. To protect against disclosure, all subjects will be assigned a unique study identification number. It is this number that will accompany study materials and data. The information that would allow for a link between this study ID number and the direct identifiers will be kept securely and separately from the datasets. All participant-identifying information will be removed from the dataset before analysis. Identifying information and de-identified paper study records will be kept in locked file cabinets and password protected computers that reside within locked offices with security personnel and other physical safeguards. All study databases will be maintained on password protected computers and routinely backed up to password protected servers. Identifying information will be deleted at the earliest possible date. We will keep all patient information confidential in accordance with Public Health Services Act (42 USC 299a-1(c)). As previously described, fetuses, neonates, minors, and prisoners are not part of this study. Pregnant women will also not be included as only people >60 years old will be eligible. Research study staff will take several steps to address the risks listed above. During screening for eligible critically ill patients, attending physicians will have the opportunity to exclude a patient who, in the physician's judgment, would not be an appropriate participant. Reasons for exclusion include (but are not limited to): legal or risk management concerns; psychological illness or morbidity; and cognitive limitations. A patient's decisional capacity will be determined by his or her treating physician using accepted standards for determining decisional capacity and will be confirmed, in a similar manner, by the research staff, as part of the informed consent process. For all participants, it will be emphasized that participation is voluntary, that all steps involved with participation are voluntary, and that they are allowed to decline to complete any activity or to answer any question they are asked. For all participants, it will be emphasized that they may withdraw from the study or any study procedures at any time without any loss of rights or benefits to which they are otherwise entitled and without losing status or standing within the institution. Healthy volunteers will receive \$50 plus the cost of parking as compensation for their time (which is estimated as up to 3 hours). Critically ill patients and their family member will not receive compensation or tokens of appreciation provided for participation to minimize potential coercion or the appearance of coercion.

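### Site-stratified blocks of 2 or 4, printed in the protocol of an unblinded trial, make many allocations guessable and expose the exploratory Day 3-6 comparison to possible selection bias

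*Combined protocol and SAP*

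**What the plan says.** All references are to the combined protocol and SAP.

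- **Aim 3, Randomization:** "After consent, patients will be randomized (1:1) to Group A vs B" through a web-based system, "with variable-sized blocks of 2 or 4, stratified by site". The proportion of blocks of each size is not given.
- **Aim 3, Blinding:** "we cannot blind patients, families, or ICU clinicians". Only the actigraphy analysis has a blinded assessor.
- **Implementation of the RCT intervention, Study design:** on Days 1 and 2 every patient wears both devices. From Day 3, patients who still need restraint stay on one device, set by the original randomization, for up to four more days. The plan says that "this design permits more prolonged comparison of novel vs. traditional device (over Days 3 to 6) to measure secondary outcomes", and regards agitation, delirium and medication use as better evaluated over that longer period.
- **Statistical Analysis Plan:** the Day 3-6 models are described as exploring long-term effects, and the secondary outcomes as hypothesis-generating.
- **Entry to the trial:** under Recruitment and Informed Consent, the ICU physicians must agree before anyone is approached. Under Protections against Risk, "attending physicians will have the opportunity to exclude a patient", for reasons that are not limited to those listed. Subject Selection makes disagreement by the treating clinicians an exclusion criterion.
- **Sample size:** "we expect to recruit 1 patient per site per month during the 18-months, yielding a total N=54". Under Minimizing missing data, "we would enroll up to 60 total patients, if needed".

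**The concern.** Concealing the list does not conceal the next allocation if staff can work it out. Here past allocations at a site can be seen at the bedside, the block rule is printed, and each site's list is short and fills slowly. A block of 2 gives away its second patient completely, and a block of 4 gives away its last two patients whenever the first two are alike.

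The within-patient comparison on Days 1-2 has little to lose, because a patient steered toward one group still wears both devices. The Day 3-6 comparison is between patients. If a physician withheld agreement for a sicker or more agitated patient because of the group expected next, the two groups would differ at baseline. That difference could be read as a device effect on agitation, delirium or medication use.

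**Working it through.** **Inputs.** From the documents: 1:1 allocation, block sizes 2 and 4, one list per site, 3 sites, 18 months, 1 patient per site per month. Assumed: a share w of blocks has size 2, with w = 0.5 as the base case because the documents give no value; the guesser knows the sizes and all earlier allocations at the site.

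**Plan's own figure.** 3 sites × 18 months × 1 per month = 54, as stated, or 18 per site.

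**Second patient in a list.** The opposite group follows with probability w × 1 + (1 − w) × 2/3. At w = 0.5 this is 0.5 + 0.333 = 0.833. It reaches 0.80 only when 2/3 + w/3 ≥ 0.80, that is, w ≥ 0.40.

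**Whole list of 18, w = 0.5.** All blocks are even-sized, so the running difference between groups is 1 before every even-numbered patient, and 0 or 2 before every odd-numbered one.

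- Even-numbered patients (9 of 18): the probability of the lagging group is always at least 0.833.
- Odd-numbered patients: certain if the difference is 2, otherwise 0.5.
- Let u be the chance that a block has just ended after k pairs. Then u₀ = 1 and uₖ₊₁ = 0.5uₖ + (1 − uₖ). The chance that the difference is 2 after pair k + 1 is uₖ × 0.5 × 1/3 = uₖ/6.
- For the nine odd positions this gives 0, 0.167, 0.083, 0.125, 0.104, 0.115, 0.109, 0.112 and 0.111, which sum to 0.926.

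Share guessable at 80% or better: (9 + 0.926)/18 = 55.1%, about 9.9 of 18 per site or 30 of 54. When the difference reaches 2, the next two allocations are both certain, so the certain share is 2 × 0.926/18 = 10.3%. Averaging the best-guess probability over all 18 positions gives 71.8%, against 50% by chance. With 20 per site (60 in total) the 55.1% becomes 55.2%.

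**Sensitivity to the unstated mix (18 per site).**

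| Share of size-2 blocks | Guessable at ≥80% | Best guess correct |
|---|---|---|
| 0 (all size 4) | 29.6% | 69% |
| 1/4 | 38.3% | 71% |
| 1/3 | 45.2% | 71% |
| 0.40 | 55.8% | 71% |
| 0.50 | 55.1% | 72% |
| 0.75 | 53.0% | 73% |
| 1 (all size 2) | 50.0% | 75% |

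**Alternative schemes (simulated, sizes equally likely and known, 18 per site).**

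| Blocks | ≥70% | ≥80% | ≥90% | Certain | Best guess correct |
|---|---|---|---|---|---|
| 2/4 | 55% | 55% | 18% | 10% | 72% |
| 4/6 | 53% | 29% | 9% | 6% | 68% |
| 4/6/8 | 54% | about 20% | 4% | about 2.5% | 67% |

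The gain lies in the more confident guesses. At a 70% threshold the schemes barely differ.

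**The case against.** Much of the case on the other side stands.

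- **Safeguards.** Screening is of consecutive patients, the PI confirms and documents eligibility, and allocation comes from a web system after consent. These reduce the risk. They do not remove it, because the physician's agreement comes before consent and the block rule is not withheld from sites.
- **Opportunity and motive.** Nothing shows that treating physicians know the block sizes or keep a site's allocation history. Both groups wear both devices on Days 1-2, so steering would change only the order and the later device. The calculation describes a diligent guesser and is best read as an upper bound on what staff would know.
- **Scope.** A reader might infer that the primary result, or all the secondary results, are compromised. The documents do not support that: agitation, delirium and medication use are also compared within patient on Days 1-2, and the between-patient analysis is labelled exploratory.
- **Recoverability.** A reader might also infer that any selection would be beyond repair. The plan collects APACHE II, Charlson, frailty, IQCODE-SF and SOFA scores, and baseline RASS, CAM-ICU and medication. Adjusting for these could correct part of it, though not selection on unrecorded clinical judgement.
- **Numbers.** Twenty-seven per group (54/2) is a ceiling for Days 3-6, because patients leave as restraint ends, or on death or ICU discharge. That attrition is a separate threat which block sizes do not touch.

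**Conclusion.** The point holds as a minor design weakness. With equally likely sizes and a guesser who tracks all 18 allocations at a site, about 55% of allocations are guessable at 80% certainty or better, 10% are certain and 72% of best guesses are right. The statement that over half are guessable at that level is conditional: it needs about 40% or more of the blocks, but not all of them, to be of size 2. At one third or one quarter the figure is about 45% or 38%. Overall accuracy lies between 69% and 75% for every mix.

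What is exposed is the exploratory between-patient comparison on Days 3-6, with at most about 27 per group. It would be going too far to call that comparison biased: the documents show a route by which selection could occur, not that it would, and no size of bias in any Day 3-6 estimate can be derived from them. The within-patient Day 1-2 comparisons, including the primary, are largely unaffected.

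**What to change.** Drop the block of 2 and use randomly varying blocks of 4, 6 and 8 within site. Replace the block sizes in the protocol with a statement that blocks vary in size, and record the sizes and their mix in a randomization document that site staff do not see. Do both, since the present sizes are already in print.

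With equal mixes, guesses at 80% or better fall from 55% to about 20% and certain guesses from 10% to about 2.5%, even if the new sizes became known. Overall accuracy falls only from 72% to 67%, and guesses at 70% or better barely change.

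The cost is one parameter in the web system and one protocol sentence. Within-site imbalance can reach 4 instead of 2. This is negligible for the primary, where every patient wears both devices. For Days 3-6 the loss is small: even if all three sites ended 4 apart in the same direction (33 against 21), relative efficiency on the numbers randomized would be 4 × 33 × 21/54² = 95%. The corresponding extreme under the present scheme (30 against 24) is 4 × 30 × 24/54² = 99%.
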